8.2.2 Accrual estimates

We estimate that roughly 125 patients with prostate cancer will be enrolled in this trial per year. Over a four-year period this will result in up to 375 patients being enrolled in the study.

8.3 Analyses Plans

8.3.1 Analysis Population

Patients with histopathology correlates will be analyzed for the Primary Aim. All remaining patients will be analyzed for the secondary endpoints.

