2.2 Secondary

- Sensitivity and PPV on a per-patient and per-region-basis (Table 1) of ⁶⁸Ga-PSMA-11 PET for detection of tumor location confirmed by histopathology/biopsy *and* conventional imaging follow-up.

- Sensitivity, specificity, and negative predictive value (NPV) on a per-patient basis of ^{68}Ga -PSMA-11 PET for detection of tumor location confirmed by histopathology/biopsy and conventional imaging follow-up.
- Detection rates on a per-patient basis of ^{68}Ga -PSMA-11 PET stratified by PSA value (0.2 - <0.5, 0.5 - <1.0, 1.0 - <2.0, 2.0 - <5.0, 5.0).
- Impact of ^{68}Ga -PSMA-11 PET on clinical management in BCR patients.
- Inter-reader reproducibility
- Safety.

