2.3.2 Secondary endpoints

- Per patient and per region detection sensitivity using a combined histology and conventional imaging correlate
- Sensitivity, specificity and negative predictive value on a per-patient basis.
- Change in management: survey based results
- Inter-reader reproducibility
- Safety: blood pressure, heart rate, self reported adverse events

3 Study Design

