5.1.1 Other Modality(ies) or Procedures

5.1.1.1 Change in management surveys

Referring clinicians will be required to fill out a pre-imaging survey within 30 days of imaging. Please see Appendix 3. Additionally within 30 days of the completion of imaging, the referring physician will be requested to fill out a post-imaging survey, and finally six months after imaging, a third survey will be filled out.

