8.3.3 Analysis of Secondary Endpoints

PPVs on a per-patient and per-region-basis of ^{68}Ga -PSMA-11 PET for detection of tumor location confirmed by histopathology/biopsy and conventional imaging follow-up will be calculated and reported along with the corresponding two-sided 95% confidence intervals. The paired McNemar's test will be used to compare the PPVs of ^{68}Ga -PSMA-11 PET imaging to the PPVs of conventional imaging.

Sensitivity, specificity, and NPVs on a per-patient basis of ^{68}Ga -PSMA-11 PET for detection of tumor location confirmed by histopathology/biopsy will be summarized in tabular format. Furthermore, the positive and negative likelihood ratios (LR+ and LR-) will be calculated and reported. Ninety-five confidence intervals of sensitivity, specificity, and NPV will be calculated using the Wilson score method. The comparisons of sensitivity, specificity, and NPV on a per-patient basis of ^{68}Ga -PSMA-11 PET imaging will be compared to of sensitivity, specificity, and NPV on a per-patient basis of conventional imaging using a paired McNemar's test.

Detection rates on a per-patient basis of ^{68}Ga -PSMA-11 PET stratified by PSA value (0.2 - <0.5, 0.5 - <1.0, 1.0 - <2.0, 2.0 - <5.0, 5.0) will be summarized in tabular format and compared between PSA strata using chi-square analysis. The impact of ^{68}Ga -PSMA-11 PET on clinical management in BCR patients will be evaluated using descriptive statistics.

9 Study Management

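### Section 8.3.1 gives the secondary endpoints only to patients without histopathology, which contradicts the plan's own secondary analyses and, read literally, drops about 25% of patients from detection and management results

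*Combined protocol and SAP*

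**What the plan says.** Section 8.3.1 has two sentences. The first sends patients with histopathology correlates to the Primary Aim. The second reads "All remaining patients will be analyzed for the secondary endpoints".

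The secondary analyses are described elsewhere as follows.

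- **Combined-reference PPV.** Section 2.2 sets the reference as "tumor location confirmed by histopathology/biopsy *and* conventional imaging follow-up". Section 2.3.2 lists "detection sensitivity using a combined histology and conventional imaging correlate". Section 8.3.3 plans PPVs "confirmed by histopathology/biopsy and conventional imaging follow-up will be calculated and reported".
- **Sensitivity, specificity and NPV.** Section 2.2 lists "Sensitivity, specificity, and negative predictive value (NPV) on a per-patient basis of" the PET scan as a secondary objective. Section 8.3.3 plans these as "confirmed by histopathology/biopsy will be summarized in tabular format".
- **PSA-stratified detection.** Sections 2.2 and 8.3.3 define it per patient in five PSA bands, with a chi-square comparison between bands. No biopsy condition is given.
- **Management impact.** Section 2.3.2 has "Change in management: survey based results". Under 5.1.1.1 "the referring physician will be requested to fill out a post-imaging survey", again without a biopsy condition. The schedule in 6.1 has none either.
- **Inter-reader reproducibility.** This is secondary in 2.2 and 2.3.2. Section 8.3.2 a) describes central collection and three readers for the data sets in the primary-endpoint analysis.
- **Safety.** This is secondary in 2.2 and 2.3.2. Sections 5.2 and 7.2 cover every patient who receives the agent.

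**The concern.** The word remaining defines the complement of the histopathology group, and 8.3.1 is the only general rule that assigns patients to the secondary endpoints. An analyst who follows it gets a secondary set without histology, although two of the secondary analyses take histology as all or part of their reference.

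For detection and management impact the outcome depends on the reader. One analyst would drop the biopsied patients and another would keep them, and both could cite the plan. An analysis-population section should settle that choice before the data are seen. It matters more here because section 1.1 intends data to be pooled across institutions for an NDA submission.

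The omission need not be neutral. Section 8.3.2 c) aims biopsy at PET-positive findings where feasible, while also leaving it to clinical indication. The omitted patients may therefore differ from the rest on the very quantity that a detection rate measures.

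**Working it through.** **1. The plan's own figures (8.2.1).** Inputs: null PPV 50%, alternative 70%, one-sided alpha 0.01, power 90%, regional prevalence 20%, biopsy share 25%.

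Normal approximation for one proportion:

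n = [(2.326 × √(0.5 × 0.5) + 1.282 × √(0.7 × 0.3)) / 0.2]² = 76.6, so 77. The plan states 75, which is close.

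Chain: 75 / 0.20 = 375 biopsies; 375 / 0.25 = 1,500 patients. The 25% share is thus the plan's own expectation.

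**2. Size of the literal secondary set.**

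- All sites: 1,500 − 375 = 1,125, so 25% are omitted.
- UCSF alone (375 patients, sections 3.2 and 8.2.2), assuming the same biopsy share: 0.25 × 375 = 93.75, about 94 omitted and about 281 left.

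**3. Each secondary analysis against the literal set.**

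| Analysis | What it needs | Under literal 8.3.1 |
|---|---|---|
| Combined-reference PPV (2.2, 2.3.2, 8.3.3) | Histology and follow-up imaging | No histology in the set |
| Sensitivity, specificity, NPV table (8.3.3) | Histology | No patient has the reference |
| Inter-reader reproducibility (2.2, 8.3.2 a) | Multiple central reads | The only data sets with described central reads are excluded |
| Safety (5.2, 7.2) | All dosed patients | Conflicts with 5.2 and 7.2 |
| PSA-stratified detection (2.2, 8.3.3) | No biopsy restriction | About 25% omitted |
| Management impact (2.2, 5.1.1.1, 6.1) | No biopsy restriction | About 25% omitted |

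**4. Effect on a detection rate.** Let q be the omitted share, d the detection rate in all patients and b the PET-positive share of the biopsied patients.

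Reported rate = (d − q·b) / (1 − q)

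Shift = −[q / (1 − q)] × (b − d)

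With q = 0.25, q / (1 − q) = 1/3. The reported rate moves 3.3 percentage points, in the opposite direction, for each 10 points by which b differs from d.

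The documents do not give b. The table is illustrative only. It uses d = 50% and 85%, the levels that section 1.2 cites from an earlier study for PSA below 1 (50%) and above 2 ng/ml (above 85%), and assumes q = 25% throughout.

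| Assumed d | Assumed b | Reported | Shift (points) |
|---|---|---|---|
| 50% | 30% | 56.7% | +6.7 |
| 50% | 50% | 50.0% | 0 |
| 50% | 60% | 46.7% | −3.3 |
| 50% | 100% | 33.3% | −16.7 |
| 85% | 65% | 91.7% | +6.7 |
| 85% | 85% | 85.0% | 0 |
| 85% | 95% | 81.7% | −3.3 |
| 85% | 100% | 80.0% | −5.0 |

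Example: (0.50 − 0.25 × 1.00) / 0.75 = 0.333. Within a PSA band, q and b take that band's own values, and neither is in the documents.

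**5. Effect on the comparison of PSA bands.** The chi-square test would rest on 1,125 patients instead of 1,500 overall. The split by band is unknown, so no power figure is given.

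**The case against.** The best reply is that exclusion is inferred. Section 8.3.1 does not say that histopathology patients are analysed only for the Primary Aim. The exclusive reading defeats much of 8.3.3, so a sensible analyst would take the remaining patients as joining the biopsied ones. The unrestricted wording for detection, the surveys scheduled for everyone, and management impact defined for patients with biochemical recurrence (which every enrolled patient has) all point to the whole cohort.

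This reply has force. The inclusive reading is plausible and may be what the sponsor meant. But no section states it, and the one sentence that defines the set says otherwise, so the contradiction stands.

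Four stronger inferences are tempting and are not supported:

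- **That detection rates will be understated.** Biopsy is aimed at PET-positive findings, which suggests b above d. But it is also done as clinically indicated, and b is not reported.
- **That confidence intervals for detection will be wider.** Section 8.3.3 plans a table and a chi-square test for this endpoint and lists no interval.
- **That restoring the biopsied patients would make sensitivity and NPV estimable.** It would not: section 8.3.2 b) says false negatives cannot be determined.
- **That other gaps add weight here.** Sections 2.2 and 8.3.3 name different references for sensitivity, specificity and NPV, and no section says which PET read defines detection for patients without central reads. Both gaps exist whatever 8.3.1 says and are separate points.

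**Conclusion.** The point holds as a contradiction in the text. Taken literally, 8.3.1 leaves the histology-referenced table without patients, takes histology out of the combined-reference PPV, removes the only data sets with described three-reader reads, and conflicts with the all-dosed safety rule. For safety the defect is one of wording, since 5.2 and 7.2 are explicit.

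The firm number is the share omitted from detection and management impact: 25%, which rests on the plan's expected biopsy rate and will move with the actual one. The possible bias in a detection rate is −(1/3)(b − d) at that share; its size and sign cannot be settled from the documents.

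A reader might infer that the primary result is compromised. It is not: the primary PPV uses the histopathology patients whichever reading is taken, and the sample size is unaffected. The matter is confined to secondary analyses and should be corrected before analysis.

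**What to change.** Replace the second sentence of 8.3.1 with wording such as:

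> All patients, including those in the primary analysis, are analysed for the secondary endpoints: all imaged patients for PSA-stratified detection; all imaged patients with the required surveys for management impact; all dosed patients for safety; all centrally read patients for inter-reader reproducibility; and, for combined-reference PPV, patients in the primary analysis together with patients whose PET-positive findings are classified by follow-up imaging under 8.3.2.

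The PPV clause assumes that either reference may classify a finding. Sections 2.2 and 2.3.2 join the two references, so the sponsor should confirm that this is what is meant.

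The cost is wording only. The restored patients are already enrolled, scanned and, under 8.3.2 a), centrally read.

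Two separate points can be settled in the same edit: reconcile the references in 2.2 and 8.3.3 for sensitivity, specificity and NPV, and state which PET read defines detection for patients without central reads. Only a decision to read those patients centrally would add work: about 1,125 scans, or 1,125 × 3 = 3,375 reads across all sites. If local reads are used for them, the report should say that the two groups were read by different methods.

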8.3.2 Analysis of Primary Endpoints

PPVs on a per-patient and per-region-basis of ⁶⁸Ga-PSMA-11 PET for detection of tumor location confirmed by histopathology/biopsy will be calculated and reported along with the corresponding two-sided 95% confidence intervals. The confidence intervals will be constructed using the Wilson score method.

a) Imaging interpretation ⁶⁸Ga-PSMA-11 PET:

PET images will initially be interpreted by a board certified nuclear medicine physician or a board certified radiologist experienced in reading PET at the time of the imaging study at the institution that the study is being performed. These interpretations will not be used for final evaluation. For the data sets included in the analysis for the Primary Endpoint, imaging data will be anonymized and collected at a central site. PET data will be interpreted by three different readers in a random order at separate reading sessions. ⁶⁸Ga-PSMA PET/CT reading training set and guides will be provided and completion of this training will be required for all central review readers.

Visual interpretation:

Regions of suspected disease will be graded on a two-point scale by each reader (0=Negative or 1= Positive). A region will be judged as positive if at least one lesion in this region is visually positive.

- i) Lymph nodes will be considered positive if the ^{68}Ga -PSMA-11 uptake is focal and greater than blood pool (adjacent or mediastinal blood pool). Pelvic lymph nodes will be subclassified according to their localization as follows: R/L obturator, R/L external iliac, R/L internal iliac and other (total of 7 subgroups).
 - ii) Visceral lesions will be considered positive if the ^{68}Ga -PSMA-11 uptake is focal and greater than physiologic background activity of the involvement organ or anatomic site.
 - iii) Bone lesions will be considered positive if the ^{68}Ga -PSMA-11 uptake is focal and greater than physiologic bone marrow.
 - iv) Prostate bed and prostate lesions will be considered positive if the ^{68}Ga -PSMA-11 uptake is focal and greater than physiologic background activity of the involvement organ or anatomic site.
- b) Follow-up Imaging:

All patients will be followed up 3-12 months with conventional imaging (dedicated CT, MRI and/or bone scan). Interpretation of follow-up imaging will be performed by local read. The follow-up conventional imaging should be the same modality/modalities as the initial staging work-up to allow for reproducible and accurate comparisons.

^{68}Ga -PSMA-11 PET positive findings will be validated as true or false positive as outlined in more detail below. False negative ^{68}Ga -PSMA-11 PET findings cannot be determined as this would require biopsies of ^{68}Ga -PSMA-11 negative but conventional or functional non- ^{68}Ga -PSMA-11 PET positive imaging lesions. Inclusion of such patients however would be violation of the inclusion criteria.

^{68}Ga -PSMA-11 PET validation based on follow-up imaging:

- i) Lymph nodes will be assessed by change in size. ^{68}Ga -PSMA-11 positive lymph nodes will be considered:
 - (1) True positive:
 - If on follow-up imaging within 3-12 months, lymph nodes seen on CT or MRI decrease by more than 30% (for patients undergoing systemic treatment of focal therapy at this site) or increase by more than 20% in short axis diameter (with a minimum of 3 mm in change in size).
 - If patients with solitary lymph node regions show a decrease of PSA by greater than 50% after targeted treatment (i.e. external beam radiation) and the lymph nodes do not change in size (less than 30% decrease or less than 20% increase in short axis diameter).
 - (2) False positive:

- If on follow-up imaging within 3-12 months, sites of initial⁶⁸Ga-PSMA-11 positive lymph node lesions seen on CT or MRI decrease by more than 30% *without* systemic therapy or focal therapy at this site.
 - If ⁶⁸Ga-PSMA-11 positive lymph node lesions do not meet the criteria for above false positive or true positive findings.
- ii) Visceral lesions (non-lymph node soft tissue or organ) will be assessed by change in size. ⁶⁸Ga-PSMA-11 positive visceral lesions will be considered:
- (1) True positive:
- If on follow-up imaging within 3-12 months, visceral lesions seen on CT or MRI decrease by 30% (for patients undergoing systemic treatment of focal therapy at this site) or increase by 20% in largest diameter.
 - If patients with solitary visceral metastasis show a decrease of PSA by greater than 50% after targeted treatment (i.e. external beam radiation) and lesions do not change in size (less than 30% decrease or 20% increase in largest diameter).
- (2) False positive:
- If on follow-up imaging within 3-12 months, sites of initial⁶⁸Ga-PSMA-11 positive lymph node lesions seen on CT or MRI decrease by more than 30% *without* systemic therapy or focal therapy at this site.
 - If ⁶⁸Ga-PSMA-11 positive lymph node lesions do not meet the criteria for above false positive or true positive findings.
- iii) ⁶⁸Ga-PSMA-11 positive bone lesions will be considered:
- (1) True positive:
- If there was a corresponding positive sclerotic lesion on the CT portion of the ⁶⁸Ga-PSMA-11 PET.
 - If there is focal uptake seen on the baseline bone scan performed within one month of ⁶⁸Ga-PSMA-11 PET.
 - If there is a lesion noted on the initial MRI performed within one month of ⁶⁸Ga-PSMA-11 PET.
 - If within 12 months follow-up CT demonstrates development of sclerosis.
 - If within 12 months follow-up MRI demonstrates a new bone lesion.
 - If within 12 months follow-up bone scan demonstrates new focal uptake.
- (2) False positive:
- If ⁶⁸Ga-PSMA-11 positive bone lesions do not meet the criteria for true positive findings.
- iv) ⁶⁸Ga-PSMA-11 positive prostate bed and prostate lesions will be considered:

(1) True positive:

- If on follow-up imaging within 12 months, lesions seen on CT or MRI decrease by 30% (for patients undergoing systemic treatment of focal therapy at this site) or increase by 20% in largest diameter..
- If patients with prostate bed lesions show a decrease of PSA by greater than 50% after targeted treatment (i.e. external beam radiation) and lesions do not change in size (less than 30% decrease or 20% increase in largest diameter).

(2) False positive:

- If on follow-up imaging within 3-12 months, sites of initial⁶⁸Ga-PSMA-11 positive lymph node lesions seen on CT or MRI decrease by more than 30% *without* systemic therapy or focal therapy at this site.
- If ⁶⁸Ga-PSMA-11 positive lymph node lesions do not meet the criteria for above false positive or true positive findings.

c) Histopathology/Biopsy:

- i) Localization of lesions for histopathology/biopsy will be classified according to the regions in table 1.
- ii) ⁶⁸Ga-PSMA-11 positive findings are aimed to be confirmed by histopathology/biopsy if clinically feasible.
- iii) Histopathological procedures and biopsies will be performed as clinically indicated and as per institutional protocol.

(1) Positive HP/Biopsy: Confirmed sites of metastatic or tumor involvement by histopathology/biopsy will be discussed with the responsible physician/surgeon.

(2) Negative Biopsy: Patients with suspected tumor recurrence on ⁶⁸Ga-PSMA-11 PET with negative histopathology/biopsy will be handled as outlined below:

(a) Lymph nodes:

- For patients undergoing nodal dissection: Patients will be rescanned with dedicated CT or MRI to determine if the suspicious ⁶⁸Ga-PSMA-11 positive node was removed.
 1. If ⁶⁸Ga-PSMA-11 positive lymph node is still present, a repeat biopsy can be pursued if clinically feasible and applicable, or follow-up using imaging as described above will be performed.
 2. If the corresponding node was removed, then this will be considered a False Positive.
- For patients undergoing needle biopsy: Images of the procedure will be reviewed to determine if the correct node was biopsied.
 1. If the correct node was biopsied, then a negative biopsy will be considered a False Positive.

2. If the incorrect node was biopsied, then follow-up imaging as described above will be performed.
 - (b) Bone lesions: Given the high rate of false negative biopsies for osseous metastases in patients with prostate cancer, patients with negative bone biopsies of PSMA PET positive lesions will be further evaluated:
 - If pathology demonstrates an alternative diagnoses that is known to be PSMA positive (eg Renal Cell Carcinoma metastases, Paget's disease), then this will be considered a False Positive.
 - If pathology is indeterminate, then follow-up imaging as described above will be performed to determine if the lesion is a True Positive or False Positive.
 - (c) Additionally a repeat ^{68}Ga -PSMA-11 can also be obtained, as allowable, in addition to repeat conventional imaging (CT and/or MRI) in cases of negative biopsy to determine if the biopsy was true negative or false negative.
 - (d) Although not routinely performed during standard practice, immunohistochemical staining for PSMA of tumor specimens (primary and lymph node metastases) may be performed, although not required.

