8.1.1 Randomization

There will be no randomization performed. There will be no blinding performed.

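### Follow-up scans that decide true or false positive are read locally with no masking to the PSMA PET result, which is expected to raise the secondary PPV by an amount the documents do not allow one to derive

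*Combined protocol and SAP*

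**What the plan says.** Section 8.3.2 treats the two sides of the PPV differently.

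- **Index test.** The PET is first read "at the time of the imaging study at the institution that the study is being performed", but that local reading is set aside for the final evaluation. For the primary-endpoint data sets, images are anonymized and collected centrally, and "PET data will be interpreted by three different readers in a random order at separate reading sessions".
- **Reference standard.** Conventional imaging (CT, MRI and/or bone scan) follows at 3-12 months, and "Interpretation of follow-up imaging will be performed by local read". No masking, reading order, central review or adjudication is given for it.

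Section 8.1.1 adds: "There will be no randomization performed. There will be no blinding performed".

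The follow-up read feeds Section 8.3.3, where per-patient and per-region PPVs "confirmed by histopathology/biopsy and conventional imaging follow-up will be calculated and reported along with the corresponding two-sided 95% confidence intervals". Section 8.3.2 c) also sends some biopsied patients to it: those whose PET-positive node is still present after dissection, those in whom the wrong node was sampled, and those with indeterminate bone pathology.

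The criteria leave different amounts of discretion. For bone, three of the six true-positive routes use follow-up imaging: new sclerosis on CT ("If within 12 months follow-up CT demonstrates development of sclerosis"), a new MRI lesion, or new bone-scan uptake. The other three use images from around the time of the PET. Nodes, visceral lesions and prostate bed lesions are judged by 20% and 30% changes in diameter. Nodes also need at least 3 mm of change.

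**The concern.** The plan guards the PET read against local influence but leaves the reference standard unprotected. When the follow-up scan is read, the PET result has existed locally for months. A reader who knows which site was positive looks there first and may accept slight sclerosis or a marginal change in diameter as confirmation. That makes the reference partly dependent on the test it is meant to verify.

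At stake is the secondary PPV, per patient and per region. Section 8.2.1 expects about 25% of patients to have a biopsy, so follow-up imaging is the main route of verification for the rest. A larger sample narrows the confidence interval but does not remove this bias. Masking cannot be restored once scans have been read with the PET result known.

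**Working it through.** **The plan's own figures.** None concerns this read. Section 8.2.1 sizes the biopsy-based PPV (50% against 70%, one-sided 0.01, 90% power) at 75. The normal approximation gives n = (2.326 × 0.5 + 1.282 × √0.21)² / 0.2² = 76.6, or 77, which is close. The plan's chain 75/0.20 = 375 and 375/0.25 = 1,500 also reproduces. This neither supports nor weakens the point, but it gives the number without biopsy: 1,500 − 375 = 1,125.

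**Effect of one-sided misreading.** Let p be the true PPV and u the share of truly false-positive findings upgraded because the reader knows the PET result. The documents give no u, so 10-20% is assumed. Apparent PPV = p + (1 − p)u.

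| True PPV | u = 10% | u = 20% |
|---|---|---|
| 50% | 0.50 + 0.50 × 0.10 = 55% | 0.50 + 0.50 × 0.20 = 60% |
| 70% | 0.70 + 0.30 × 0.10 = 73% | 0.70 + 0.30 × 0.20 = 76% |

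**Effect of misreading both ways.** If a share d of true positives is also downgraded, apparent PPV = p(1 − d) + (1 − p)u. With u = d = 10%, 50% stays at 0.45 + 0.05 = 50%, and 70% falls to 0.63 + 0.03 = 66%. Net inflation needs (1 − p)u > pd: u > d at p = 50%, and u > 0.7/0.3 = 2.3 times d at p = 70%.

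**Against sampling error.** Section 1.2 cites detection rates of 50% (PSA below 1 ng/ml) and above 85% (PSA above 2 ng/ml). Using 50% and 85% as a rough range, 1,125 × 0.50 = about 560 and 1,125 × 0.85 = 956 patients without biopsy would be PET-positive, assuming all have usable follow-up. Wilson 95% half-widths:

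- Pooled, PPV near 55%: 4.1 points (n = 560) and 3.2 points (n = 956), against an assumed bias of 5-10 points.
- Pooled, PPV near 73%: 3.7 and 2.8 points, against 3 points at u = 10%. Near 76%: 3.5 and 2.7 points, against 6 points at u = 20%.
- Per region, taking the 15-35% shares in Section 8.2.1 as a rough split, n runs from 0.15 × 560 = 84 to 0.35 × 956 = 335. The half-width near 55% is about 10 to 5 points, similar in size to the assumed bias.

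Section 8.3.3 asks for 95% intervals on the secondary PPV without naming the method. Wilson is used here because the plan names it for the primary PPV.

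**The case against.** The strongest reply is that the plan already limits discretion and that nothing shows the bias to be large. Much of this stands.

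- Diameter cut-offs, and the 3 mm minimum for nodes, restrict borderline calls. Which lesion and slice to measure still rests with the reader.
- Some true-positive routes need a PSA fall of more than 50% after targeted treatment. None of these applies to bone.
- Node and bone findings that meet no true-positive rule default to false positive, which pushes PPV down. The default operates only when no confirming call is made, so it does not prevent one.
- Three bone routes use images from around the time of the PET, which the sentence on follow-up reading does not cover.

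A reader might also infer more than the documents support:

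- **That the plan orders unmasked reading.** "There will be no blinding performed" stands under the randomization heading of an open-label study with no randomization, and does not mention image readers. The plan is silent on masking the follow-up read.
- **That the same person reads both scans.** The plan says only that the read is local. Nothing requires this, and nothing prevents it.
- **That the bias exceeds the reported uncertainty.** Across the whole assumed range, this is shown only for the pooled PPV near 50%.
- **That the comparison with conventional imaging favours PET.** No direction can be claimed. Follow-up uses the same modalities as the initial work-up, which could favour conventional imaging instead.
- **That the primary PPV is inflated.** It rests on histopathology. The plan does not say whether biopsied patients sent on to follow-up imaging count in it.

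**Conclusion.** The point holds as a gap in the design of the secondary PPV. The read that settles true or false positive is local, the PET result is already available locally, and no provision masks or orders that read. The expected direction is upward, provided errors tilt toward confirmation, as knowledge of a positive PET would favour. Exposure is greatest for bone, which has the largest anticipated share of disease (35% in Section 8.2.1) and follow-up criteria without a threshold. It is smaller where size cut-offs, a PSA fall or the default to false positive apply.

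The size is unknown. The 5-10 points at a PPV of 50% and 3-6 points at 70% rest on an assumed 10-20% upgrade rate applied to all false positives, with no offsetting errors. They are an illustration, not an estimate. The case for acting is that the remedy is cheap and cannot be applied after the reads are done.

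**What to change.** In Section 8.3.2 b), keep the local read and fix its order:

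1. The follow-up reader records lesions and diameters, by region, on the baseline and follow-up conventional scans before opening the PSMA PET images or report. Where existing staffing allows, this is someone who did not report the PET. No added reader is required.
2. The PET report is withheld from that reader only, until the form is complete. Clinical care and the 30-day post-imaging survey are unaffected.
3. PET-positive sites are then matched by location. Findings added or re-measured at this step are flagged.
4. In Section 8.3.3, report the secondary PPV with and without flagged findings.
5. In Section 8.1.1, clarify that the statement on blinding does not refer to this read.

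The cost is one extra form and a reading-order instruction, with no new scan. The downside is that small lesions may appear only at the flagged step, so the PPV without flagged findings is a conservative lower figure. The bone route that uses the CT portion of the PET lies outside this step.

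### Read literally, Section 8.3.2 counts an unbiopsied PET-positive lymph node followed by bone scan alone as a false positive, whatever its true state

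*Combined protocol and SAP*

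**What the plan says.** All the relevant text is in Section 8.3.2 of the combined protocol and SAP.

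- **Follow-up modality, part b).** "All patients will be followed up 3-12 months with conventional imaging (dedicated CT, MRI and/or bone scan". The next instruction on modality is: "The follow-up conventional imaging should be the same modality/modalities as the initial staging work-up to allow for reproducible and accurate comparisons". Bone scan alone therefore meets the follow-up requirement if that was the staging work-up.
- **Lymph nodes, basis of the verdict.** "Lymph nodes will be assessed by change in size".
- **Lymph nodes, true positive.** One route needs a size change on cross-sectional imaging: "lymph nodes seen on CT or MRI decrease by more than 30" per cent under treatment, or an increase of more than 20%. The other needs a PSA fall of more than 50% after targeted treatment "and the lymph nodes do not change in size (less than 30% decrease or less than 20% increase in short axis diameter").
- **Lymph nodes, false positive.** Besides shrinkage without therapy, there is a residual clause for the case where "positive lymph node lesions do not meet the criteria for above false positive or true positive findings".
- **Visceral and prostate-bed lesions, true positive.** The structure is similar. The prostate-bed rule, for example, opens "If on follow-up imaging within 12 months, lesions seen on CT or MRI decrease by 30" per cent. The false-positive bullets in both places are worded for lymph nodes.
- **Bone.** This is the only site whose rules use bone scan as evidence.

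Section 8.3.3 uses histology and imaging follow-up together for the secondary PPV. Section 8.3.1 restricts the Primary Aim to patients with histopathology.

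**The concern.** The follow-up instruction and the verdict rules do not fit together. A site can follow part b) as written, repeat the bone scan that was the staging work-up, and so hold no size measurement for a PET-positive node. The rules have no outcome for a node that could not be assessed, so it drops into the residual clause and is scored as a PET error. The patient has missed nothing; the error comes from the rule.

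What is at stake is the secondary PPV. Part of it would then reflect which modality was used for staging instead of how PET performed. Local practice may differ between centres, and Section 1.1 intends the data to be pooled across institutions for a marketing application.

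**Working it through.** **Tracing one patient.** Take a patient staged by bone scan alone who has a PET-positive node and no biopsy.

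1. Part b): a repeat bone scan satisfies both the list of modalities and the same-modality instruction.
2. True positive by size change: this needs CT or MRI at follow-up, so it is not met.
3. True positive by PSA: no modality is named, but the node must be shown to be stable in short-axis diameter. A bone scan does not give that diameter, so it is not met.
4. False positive by untreated shrinkage: this also needs CT or MRI, so it is not met.
5. Residual clause: no criterion is met, so the verdict is false positive.

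A malignant node and a benign node reach the same verdict. The benign one is classed correctly by accident and the malignant one wrongly, so the error runs in one direction only.

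For an unmeasured visceral or prostate-bed lesion, steps 2 and 3 fail in the same way. The false-positive bullets there speak of lymph nodes, so read literally the lesion receives no verdict.

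**Reach into the primary PPV.** Section 8.3.2 c) sends some biopsy outcomes back to follow-up imaging, for example when the wrong node was needled. Only through such referrals can the clause affect the primary PPV.

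**Size.** The plan gives no figure on this point, so there is none to reproduce. The following is an illustration.

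- True node PPV: 70%, an assumption borrowed from the alternative in Section 8.2.1. (That section's own calculation reproduces closely: (2.326 × 0.5 + 1.282 × 0.4583)² / 0.2² = 76.6, against 75 stated.)
- Share of nodes with a biopsy verdict: 25%, an assumption. Section 8.2.1 expects about 25% of patients to be biopsied and gives no figure per node. The true PPV is taken to be the same with and without biopsy.
- f: the share of imaging-judged nodes that would be true positive if measured but have no size-capable follow-up. The documents do not give it.

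Observed PPV = 0.25 × 0.70 + 0.75 × 0.70 × (1 − f) = 0.70 × (1 − 0.75f)

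| f | 1 − 0.75f | Observed PPV | Loss (points) |
|---|---|---|---|
| 5% | 0.9625 | 67.4% | 2.6 |
| 10% | 0.925 | 64.8% | 5.2 |
| 20% | 0.85 | 59.5% | 10.5 |

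With no biopsy verdicts at all, 0.70 × (1 − f) gives 66.5%, 63.0% and 56.0%.

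**The case against.** The best defence is that part b) says follow-up should match the staging modality, which recommends comparability and does not prohibit anything else. The soft-tissue rules name CT or MRI, so a sensible site would obtain one. Biopsy is a further route to a verdict, and Section 8.3.2 c) aims for it where feasible. Every patient also has a PET/CT or PET/MRI, so a cross-sectional baseline of some kind exists.

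Much of this stands. A reader might infer that such lesions cannot be scored at all, and the text does not go that far. But nothing in part b) tells a site to add CT or MRI for a PET-positive soft-tissue site. About 75% of patients are expected to have no biopsy. A baseline scan alone shows no change. The CT component of the PET is named as evidence only in the bone rules, and the residual clause applies whenever the measurement is absent.

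Three stronger readings should be set aside:

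- **Coverage.** It is tempting to add the patient staged by pelvic MRI whose PET-positive node lies outside the pelvis. Part b) ties modality and does not tie coverage, so an MRI that covers the node complies.
- **Three of four regions.** Section 8.2.1 places 30% + 15% + 20% = 65% of disease outside bone. That does not measure the bias: the false-positive default as worded covers nodes only, and the percentages describe disease, not PET findings.
- **Erosion of the 50% to 70% margin.** That null and alternative belong to the histopathology-based primary PPV. Section 8.3.3 sets no 50% threshold for the composite, only confidence intervals and a comparison with conventional imaging.

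**Conclusion.** The conflict is real and does not depend on f: a stated rule can give a wrong verdict on a node in a patient who complied with follow-up. It is confined to PET-positive nodes judged by imaging without a size measurement, and it acts mainly on the secondary composite PPV. The related defect for visceral and prostate-bed lesions is a missing verdict, not a downward bias.

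Under the stated assumptions the loss is about 2.6 to 10.5 percentage points for f from 5% to 20%. If f is close to zero, it is negligible. The documents do not say how often patients are staged by bone scan alone. They do not define the initial staging work-up, and neither the eligibility criteria (Section 3.3.1) nor the schedule (Section 6.1) lists conventional imaging. A difference in bias between sites is therefore possible but not demonstrated. The point should be corrected before lesions are classified; it does not undermine the primary analysis.

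**What to change.** Reconcile part b) of Section 8.3.2 with the validation rules that follow it:

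1. State that the same-modality sentence is a preference for comparability and does not override the CT or MRI measurement that the soft-tissue rules rely on.
2. Limit the residual false-positive clause to lesions with both a baseline and a follow-up size measurement.
3. Class PET-positive soft-tissue lesions (nodal, visceral, prostate bed) that have neither such measurements nor histology as not evaluable, and exclude them from the main composite PPV.
4. Report the number of not-evaluable lesions by site, and add a sensitivity analysis counting them as false positives.

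This is mainly a classification rule and need not change any patient's imaging. The cost is a few sentences, one added sensitivity analysis and a somewhat smaller denominator. If the unmeasured share is the same f among all imaging-judged nodes and 25% have a biopsy verdict, the node denominator falls by 0.75f: 3.75%, 7.5% or 15% at f = 5%, 10% or 20%. The main estimate then assumes that lack of a measurement is unrelated to whether the node is malignant. The sensitivity analysis gives the lower bound if that assumption fails.
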